6. TRIAL OBJECTIVES AND ENDPOINTS

6.1. Objectives

6.1.1. Primary Objective

• To assess the objective response rate (ORR; complete response + partial response [CR + PR]) of tazemetostat in combination with rituximab in subjects with R/R FL and with WT EZH2 status.

6.1.2. Secondary Objectives

- To evaluate the safety of the combination of tazemetostat and rituximab by assessing the incidence of adverse events/serious adverse events, change of vital signs, lab results, and physical exam findings from baseline
- To estimate median progression-free survival (PFS) of tazemetostat in combination with rituximab at 2 years in subjects with R/R FL and WT EZH2 status, and in the pooled group regardless of mutation status.
- To explore the response rate in a subset of subjects with MT EZH2.
- Evaluation of efficacy outcomes in rituximab refractory subjects

6.1.3. Exploratory Objective

• To estimate the OS of subjects receiving tazemetostat in combination with rituximab

6.2. Endpoints

6.2.1. Primary Endpoint

• ORR, defined as the proportion of all subjects with WT EZH2 status achieving a CR or PR according to the 2014 Lugano Classification (Appendix 3) as assessed by Investigator and blinded independent review committee (IRC) at the following time points: Cycle 3, Cycle 6, Cycle 12, Cycle 18, and Cycle 24

6.2.2. Secondary Endpoints

- Type, frequency, severity, timing of onset, duration, and relationship to study drug of any TEAEs or abnormalities of laboratory tests; SAEs; dose limiting toxicities (DLTs), or AEs leading to discontinuation of study treatment or death.
- PFS, defined as the time from first dose of study drug to the time of the earliest date of CR or PR per the 2014 Lugano Classification (Appendix 3) or death, whichever occurs first, as assessed by an IRC.
- Duration of response (DOR), defined as the time from the earliest date of CR or PR per the 2014 Lugano Classification (Appendix 3) to documented progression or death, whichever comes first, as assessed by an IRC.

- ORR in the pooled group regardless of mutation status and in a subset of subjects with MT EZH2 at the following time points: Cycle 3, Cycle 6, Cycle 12, Cycle 18, and Cycle 24 for tazemetostat in combination with rituximab using 2014 Lugano Classification (Appendix 3).
- ORR in rituximab refractory subjects at the following time points: Cycle 3, Cycle 6, Cycle 12, Cycle 18, and Cycle 24 for tazemetostat in combination with rituximab using 2014 Lugano Classification (Appendix 3).

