- 13. Other diagnosis of cancer that is likely to require treatment in the next 2 years, with the exception of the following:
 - a. Curatively treated basal cell carcinoma or squamous cell carcinoma of the skin
 - b. Curatively treated carcinoma in situ of the cervix
 - c. Hormonal therapy for prostate cancer
- 14. Females who are pregnant or lactating/breastfeeding
- 15. Received a live virus vaccination within 28 days of first dose of rituximab
- 16. Participation in a separate investigational therapeutic study
- 17. Psychiatric illness/social situations that would interfere with study compliance

Investigational Product, Dosage, and Mode of Administration:

Subjects will receive open-label tazemetostat 800 mg twice daily starting on Cycle 1 Day 1 until the end of Cycle 24, for 24 months of therapy or until disease progression, unacceptable toxicity, or withdrawal of consent. Tazemetostat is to be supplied by Epizyme in pre-counted, appropriately labeled bottles.

Subjects will also receive open-label rituximab, administered by either subcutaneous injection or IV infusion according to the regional product prescribing information, labeling, and institutional guidelines, on Days 1, 8, 15, and 22 of Cycle 1 and then on Day 1 of Cycles 3 through 6, accounting for an additional 4 doses (ie, a total of 8 doses of rituximab in 6 cycles). Rituximab will not be provided and will be procured by the clinical sites from commercial sources.

Duration of treatment:

Subjects will be treated in 28-day cycles with tazemetostat in combination with rituximab through Cycle 6 then tazemetostat alone through Cycle 24, for 24 months of therapy or until disease progression, unacceptable toxicity, or withdrawal of consent.

Criteria for Evaluation:

Efficacy:

Disease response rate (ORR) at the following time points: Cycle 3, Cycle 6, Cycle 12, Cycle 18, and Cycle 24 for tazemetostat in combination with rituximab using the Lugano 2014 Classification (Appendix 3). Other efficacy endpoints will be PFS and DOR, with disease progression defined by 2014 Lugano Classification.

Safety

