Safety will be assessed through summaries of AEs, laboratory evaluations, vital signs, and physical examinations. Safety analyses will be based on all enrolled subjects who receive at least 1 dose or partial dose of study drugs (safety population). Drug exposure will be summarized by descriptive statistics. Severity of all AEs is to be evaluated by the Investigator based on the CTCAE, version 5.0 and will be coded to preferred term, higher level term, and system organ class using the Medical Dictionary for Regulatory Activities (MedDRA; version 23.1). The number and percentage of subjects with AEs will be presented by MedDRA system organ class and preferred term, relationship to study treatment, and severity. Descriptive statistics will be used rather than inferential statistics. Laboratory values also will be classified by toxicity grade based on the NCI's CTCAE, version 5.0. Laboratory shift tables of the baseline results to each of the subsequent visits will be produced.

Statistical Methods:

Primary Efficacy Endpoint - All Phase 2 Cohorts

• ORR: ORR is defined as the proportion of the FAS subjects with WT EZH2 status achieving a CR or PR according to the 2014 Lugano Classification (Appendix 3) as assessed by Investigator and blinded IRC at the following time points: Cycle 3, Cycle 6, Cycle 12, Cycle 18, and Cycle 24. Subjects with a best response of unknown/non-evaluable response will be treated as non-responders, (i.e., they will be

Name of Investigational Product: Tazemetostat (EPZ-6438)

Name of Active Ingredient: Tazemetostat

included in the denominator when calculating the percentage). ORR will be presented with corresponding 2-sided 95% CIs. This analysis will be performed on a subset of the FAS that includes all subjects with WT EZH2 status.

Secondary Efficacy Endpoints:

- **PFS:** The PFS, defined as the time from the first dose of study drug to the earliest date of disease progression per the 2014 Lugano Classification (Appendix 3) or death from any cause, whichever occurs first, will be assessed by IRC. PFS will be estimated using Kaplan-Meier method and presented with corresponding 2-sided 95% CIs. PFS will be analyzed using the FAS.

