- Tumor response assessments by disease-appropriate standard criteria (2014 Lugano Classification [Appendix 3]) using ¹⁸FDG-PET and CT, or combined as PET-CT, of known sites or newly suspected sites of disease (neck, chest, abdomen, and pelvis required at all time points). MRI instead of CT if clinically indicated. Additional imaging of brain or bone by MRI or CT if clinically indicated at screening and during the study for CNS signs/symptoms or bone marrow involvement. Radiologic tumor assessments will be performed at screening between day -28 and day -1 and at specified time points (±7 days) during study treatment beginning from start of treatment (C1D1), irrespective of treatment delays, until loss of clinical benefit or disease progression (i.e., C3D1, C6D1, C12D1, C18D1, C24D1, etc). CT imaging (as PET-CT or CT alone) must include diagnostic quality CT scan AND should preferably be contrast enhanced; FDG-avid disease should report PET-CT based response, non FDG-avid disease should report CT based response. Tumor assessment at EOT required if no disease progression previously documented. Subjects who discontinue study treatment for any reason other than disease progression will continue to undergo tumor response assessments at timepoints (±7 days) as scheduled until disease progression. A standard-of-care clinical examination for lymphoma, including assessment of B symptoms, will be performed at screening and with tumor assessments (See Section 11).
- ^m CT of neck, chest, abdomen, and pelvis required at screening then during study treatment (±7 days) at C3D1, C6D1, C12D1, C18D1, and C24D1, as well as EOT. If no disease progression previously documented and subject continues treatment with tazemetostat beyond 24 cycles, CT will be required every 6 months (±7 days) at C30D1, C36D1, etc. During Survival Follow-up, CT performed every 6 months (±30 days) for 2 years then every 12 months (±30 days) thereafter, or until disease progression (See Section 11).

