14.3. Secondary Efficacy Analyses

PFS is defined as the time from the first dose of study drug to the earliest date of documented disease progression per the 2014 Lugano Classification (Appendix 3) or death from any cause, whichever occurs first. Disease progression will be assessed by a blinded IRC. Cases without a reported PFS event will be censored at the time of the last tumor assessment. Median PFS, first and third quartiles will be estimated using Kaplan-Meier method on the FAS, if there are a sufficient number of PFS events (ie, relapses, progressions or deaths), and 2-sided 95% CIs will be estimated. Figures and listings of PFS will also be provided.

For each subject with a CR or PR, DOR is defined as time from the earliest date of CR or PR per the 2014 Lugano Classification (Appendix 3) to documented disease progression or death, whichever occurs first. DOR will be assessed by a blinded IRC If there are a sufficient number of responders who subsequently progress or die due to any cause. The median DOR, first and third quartiles, will be calculated from the Kaplan-Meier estimates using the FAS. The associated 2-sided 95% CIs will be estimated. A listing of DOR will be provided.

Analysis of ORR as a secondary endpoint will be similar to analysis of the primary efficacy endpoint but performed on FAS regardless of mutation status and the defined subgroups (MT EZH2 or rituximab refractory subjects).

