14.6. Determination of Sample Size and Criteria for Early Stopping Due to Futility

The primary objective of this study is to evaluate the ORR obtained in subjects with R/R FL and WT EZH2 status, treated with the combination of rituximab and tazemetostat. Given the historical data with single agent rituximab (McLaughlin, 1998; Leonard, 2019), the Sponsor would consider the combined regimen to be of no further interest if the ORR were 50% or less, but of considerable interest if the ORR were at least 70%.

Simon's two-stage design (Simon, 1989) will be used. The null hypothesis that the true response rate is 50% will be tested against the one-sided alternative. In the first stage, 15 subjects will be accrued. If there are 8 or fewer responses in these 15 subjects, the regimen will be considered as futile.

Subject enrollment will continue during futility analysis. If 9 responses or greater (CR + PR) are seen in the initial 15 subjects, additional subjects will be accrued for a total of 54 evaluable subjects. The Sponsor expects 80% of enrolled subjects to have WT EZH2 status. Consequently, the study will enroll approximately 43 WT subjects as well as approximately 11 MT subjects. With an estimated early dropout rate of 10%, this study estimates a total accrual of 59 subjects.

For the primary analysis, the null hypothesis will be rejected if 27 or more responses (CR + PR) are observed in the first 43 evaluable subjects regardless of mutation status. This design yields a one-sided type I error rate of 0.05 and power of 0.801 when the true response rate is 70%.

If the primary analysis is successful, full analysis will be conducted once 54 evaluable subjects are available regardless of mutation status. Subjects in the FAS will be stratified to 2 subgroups depending on their EZH2 mutation status (WT vs MT).

With an estimated 54 eligible subjects in the combined FAS, rates of individual AEs can be estimated to within at most \pm 14% (95% confidence interval). Any AE with a true rate of at least 5% is likely to be observed at least once (93% chance).

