Assuming accrual takes place over 24 months, with at least an additional 12 months of follow-up for progression, there would be approximately 65% power to rule out a benchmark median PFS of 12 months against the alternative of a true PFS of 18 months (one-sided, 0.05 level test) in the primary analysis subset of 43 subjects with at least 26 PFS events. If PFS is similar in both subsets regardless of EZH2 status, then there would be 80% power for the same analysis in the combined FAS of 54 subjects with at least 33 PFS events.

The reporting of response rate in the MT EZH2 subset (anticipated to be 11 subjects) will have very little precision and is exploratory only. Note, the subjects with MT EZH2 status will be included in all primary safety analyses.

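### The protocol's endpoint lists end PFS at first CR or PR (or death), its analysis text ends it at progression or death, and SAP 4.2 names no event

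*Protocol*

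**What the plan says.** The protocol defines the PFS event in four places, and they fall into two groups.

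- **Endpoint lists.** Section 6.2.2 has "PFS, defined as the time from first dose of study drug to the time of the earliest date of CR or PR" under Lugano 2014, or death if that comes first. The secondary endpoints in the Synopsis carry the same definition.
- **Analysis text.** The statistical methods in the Synopsis measure PFS from "the first dose of study drug to the earliest date of disease progression per the 2014 Lugano Classification", or death from any cause. Section 14.3 agrees: "PFS is defined as the time from the first dose of study drug to the earliest date of documented disease progression", or death from any cause. It also spells out what counts, namely "PFS events (ie, relapses, progressions or deaths".

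Two other places side with the analysis text. The Synopsis criteria for evaluation say "Other efficacy endpoints will be PFS and DOR, with disease progression defined by 2014 Lugano Classification". The PFS power paragraph in Section 14.6 assumes follow-up for progression.

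SAP Section 2 says that the SAP is read together with the protocol and supersedes its statistical considerations. The opening of protocol Section 14 gives the SAP precedence where the two are inconsistent. SAP 4.2 lists PFS as assessed by a blinded IRC and gives neither a start date nor an event.

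**The concern.** A response is the opposite of a PFS event. Taken literally, Section 6.2.2 turns PFS into time to first response or death. A responder's PFS would end on the date that the next bullet of the same section uses as the start of duration of response. A non-responder who progresses would have no event at progression and would stay at risk until death or censoring. A more active regimen would tend to show a shorter PFS, the reverse of what the comparison of 12 and 18 month medians in Section 14.6 is meant to measure.

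An analyst working from Section 14 would use progression. Someone taking the definition from the formal endpoint list would not. The document that claims precedence does not choose between them.

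**Working it through.** **1. Which definition does the planning figure assume?** Section 14.6 gives about 65% power at one-sided 0.05 for a median of 18 against 12 months, "in the primary analysis subset of 43 subjects with at least 26 PFS events". With a one-sample exponential model on the log hazard:

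- power = Φ(√d × ln(18/12) − z₀.₉₅)
- d = 26: √26 × 0.4055 − 1.645 = 2.067 − 1.645 = 0.42, so power = 66.4%, within 2 points of the stated figure.

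Expected events were checked under exponential PFS with median 18 months, uniform accrual over 24 months and 12 more months of follow-up:

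- P(event) = 0.589
- 43 × 0.589 = 25.3, against 26 stated
- 54 × 0.589 = 31.8, against 33 stated

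The planning is therefore on a progression scale. (The same formula gives 75.3% at 33 events, not the stated 80%. That is a separate matter and nothing here depends on it.)

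**2. One subject under each definition.** Cycles are 28 days. Section 7.7 times scans "beginning from start of treatment (C1D1), irrespective of treatment delays", with a window of ±7 days. One month is taken as 30.44 days.

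| Scan | Study day | Months | Months with ±7 days |
|---|---|---|---|
| Cycle 3 Day 1 | 2 × 28 + 1 = 57 | 57/30.44 = 1.87 | 50/30.44 = 1.64 to 64/30.44 = 2.10 |
| Cycle 24 Day 1 | 23 × 28 + 1 = 645 | 645/30.44 = 21.2 | 638/30.44 = 20.96 to 652/30.44 = 21.42 |

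A subject who responds at the first of these scans and is progression-free at the second has PFS of about 1.9 months under Section 6.2.2. Under Section 14.3 the same subject has at least about 21 months.

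**3. The median.** Cycle 6 Day 1 is study day 5 × 28 + 1 = 141, or 141/30.44 = 4.6 months. Assume that at least half of subjects have responded by then; the design works with response rates of 50% and 70%. The median of the Section 6.2.2 quantity would then be about 4.6 months or less. That cannot be read against medians of 12 and 18 months.

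**4. Counts.** Section 14.6 says "the null hypothesis will be rejected if 27 or more responses (CR + PR) are observed in the first 43 evaluable subjects".

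- Every responder is alive at response, so 27 responses are 27 events under Section 6.2.2: 27/43 = 62.8%.
- The PFS planning has 26 events in 43: 26/43 = 60.5%.
- 27 − 26 = 1 more event than planned, before any progression is counted.
- 43 − 27 = 16 non-responders would have no event at progression.

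This sets counts side by side and nothing more. The 43 in the response rule are regardless of mutation status, and the PFS paragraph does not say whether its 43 are the same subjects. It also assumes one assessor for response and PFS.

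**5. Does another provision resolve it?** Nothing ranks protocol Section 14 above Section 6. The SAP would govern, but it is silent on the event.

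**The case against.** The strongest reply is that this is an editorial slip which the protocol already answers. Section 14.3 gives the event, the censoring rule, the Kaplan-Meier method and a list of events. The Synopsis statistical methods agree. The SAP is to be read with the protocol, so where it is silent Section 14.3 can still supply the definition. No PFS analysis will be run, so a missing event in SAP 4.2 affects no output.

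Most of that is fair, and it limits the weight of the point. It does not remove the contradiction. The formal endpoint lists still state a rule that reverses the meaning of the endpoint, and they do so twice in full sentences.

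It can also be said that 27 against 26 is a coincidence, since one number is a rejection boundary for response and the other comes from a survival calculation. The 43 in the PFS paragraph may well be the wild-type subjects, because the paragraph goes on to contrast them with the combined 54. That stands: the count illustrates the literal reading and is not an effect size. The one-subject example carries the argument.

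**Conclusion.** The concern holds. The Synopsis endpoint list and Section 6.2.2 are wrong as written, and the Synopsis statistical methods and Section 14.3 are right. That the error was carried over from the neighbouring definition of duration of response is likely, but it is an inference.

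The gap for a single early and durable responder is about 1.9 against at least about 21 months. It rests only on 28-day cycles and the scan schedule. The median of about 4.6 months or less rests further on at least half of subjects responding by Cycle 6 Day 1.

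The stated PFS power is unaffected because it already assumes progression. No reported result is affected either: SAP Sections 5.2, 8 and 9 record 5 treated patients and no efficacy analysis. The point concerns the consistency of the documents and should be fixed on that basis.

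**What to change.** In the PFS bullets of the Synopsis endpoint list and Section 6.2.2, replace the reference to CR or PR with documented disease progression under Lugano 2014, and make the death component death from any cause, so that both match Section 14.3. State the same start date and event in SAP 4.2.

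A minor addition, on which the point above does not depend: PFS and duration of response name only an IRC as assessor, while Section 11.3 convenes an IRC only if the data are promising. One line should say which assessments are used if none is convened. The investigator assessments already recorded under Section 11.1 are the available source. If the sponsor chooses them, the line should note that they are more open to bias than blinded review in an open-label, single-arm trial.

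The cost is wording only: no new data, image reads or subjects. With the trial ended, the change affects the documents and not the outputs.

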6.2.3. Exploratory Endpoint

• OS, defined as the interval of time between the date of the first dose of study drug and the date of death due to any cause

7. INVESTIGATIONAL PLAN

7.1. Overall Study Design and Plan

[figure not shown]
This is a phase 2, multicenter, open-label study of oral tazemetostat in combination with rituximab in subjects with R/R FL. Subjects will enroll into a single, open-label arm of the study where they will each be stratified based on EZH2 mutation status (MT or WT). Additionally, subjects will be stratified by previous experience with rituximab (rituximab refractory or rituximab-naïve). Stratification will occur during data analysis rather than at enrollment. This study is designed to evaluate the safety and efficacy of tazemetostat in combination with rituximab in subjects previously treated with at least 2 prior systemic lines of therapy for FL and features early futility stopping to maintain subject safety.

The first stage will enroll 15 subjects regardless of EZH2 mutational status. Futility analysis will be performed when the Cycle 6 Day 1 tumor assessment data are available for the first 15 subjects. If there are 8 or fewer responses in these 15 subjects, the study will be considered futile. Enrollment will continue during the interim futility analysis. If 9 responses or greater are seen in the initial 15 subjects, additional subjects will be accrued for a total of 54 evaluable subjects regardless of mutation status.

Based on Simon's 2-stage design, the primary analysis will occur after 43 evaluable subjects regardless of mutation status are available. Enrollment will continue during the primary analysis. Full set analysis will occur once data from 54 evaluable subjects regardless of mutation status are available.

This study includes a 28-day screening period, a 2-year (24-cycle) treatment period, and a follow-up period. During the treatment period, subjects will receive tazemetostat in combination with rituximab in 28-day cycles for the first 6 cycles followed by tazemetostat alone in 28-day cycles for the remaining 18 cycles, or until disease progression, unacceptable toxicity, or withdrawal of consent. Disease assessments will be performed at screening, Cycle 3 Day 1, Cycle 6 Day 1, Cycle 12 Day 1, Cycle 18 Day 1, and Cycle 24 Day 1.

Figure 1: Study Schema

Note: Enrollment will not stop during futility analysis or primary analysis.

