13. BIOMARKER ASSESSMENTS

14. STATISTICS

This section is a summary of the planned statistical analyses of the most important endpoints including primary and key secondary endpoints. A statistical analysis plan (SAP) will be finalized prior to final database lock. Should the SAP and the protocol be inconsistent with respect to any further planned analyses, the language of the SAP is governing.

All statistical analyses will be performed by the Sponsor or designee. Sample and power calculations are based on nQuery 8.0.

Definitions of Analysis Sets

The analysis sets will be defined as follows:

- Futility Analysis Set will comprise of the first 15 subjects regardless of EZH2 status who received at least 1 dose of study drug and had tumor assessment at both baseline and Cycle 6.
- **Primary Analysis Set** will comprise of the first 43 subjects regardless of EZH2 status who received at least 1 dose of study drug and had tumor assessment at both baseline and at least one post-baseline timepoint (Cycle 3, Cycle 6, Cycle 12, Cycle 18, and Cycle 24).
- Full Analysis Set (FAS) will include all subjects who received at least 1 dose of study drug and had tumor assessment at baseline and at least one post-baseline timepoint (Cycle 3, Cycle 6, Cycle 12, Cycle 18, and Cycle 24). This will be the overall analysis set for efficacy evaluations.
- Safety Population will include all subjects who received at least 1 dose of the study drug and have at least 1 post-baseline safety evaluation, regardless of mutation status. This will be the analysis set for all safety evaluations.

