14.1. Futility Analysis

Futility analysis (FA) will be performed when the Cycle 6 tumor assessment data are available for the first 15 evaluable subjects regardless of EZH2 status. ORR, defined as the proportion of the subjects achieving a CR or PR according to the 2014 Lugano Classification (Appendix 3), will be calculated. Subjects with the best response of unknown/non-evaluable response will be treated as non-responders, (i.e., they will be included in the denominator only when calculating ORR).

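### The futility look waits for all 15 Cycle 6 scans while enrolment runs on, although seven non-responders already settle it; given a futile look, about 3 enrolments are avoidable at a 50% response rate

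*Protocol*

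**What the plan says.** Protocol Section 7.1 fixes the time of the look: "Futility analysis will be performed when the Cycle 6 Day 1 tumor assessment data are available for the first 15 subjects". The boundary is: "If there are 8 or fewer responses in these 15 subjects, the study will be considered futile". Accrual is not held: "Enrollment will continue during the interim futility analysis", and the note under the study schema extends this to the primary analysis: "Note: Enrollment will not stop during futility analysis or primary analysis". The synopsis gives the same timing, and Section 14.6 and SAP Section 3.2.1 repeat the continued enrolment.

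Section 14 defines the Futility Analysis Set as the first 15 dosed subjects, of either EZH2 status, who "had tumor assessment at both baseline and Cycle 6". Section 14.1 adds: "Subjects with the best response of unknown/non-evaluable response will be treated as non-responders".

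Neither document provides for declaring futility before the fifteenth Cycle 6 assessment. Protocol Section 7.6 lets the sponsor stop the study at any time for any reason, but ties that to no response count.

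**The concern.** Nine responses in 15 are needed to continue. Once seven of the 15 are known not to have responded, the remaining scans cannot change the decision. The plan still waits for them, and subjects keep entering a planned 24-cycle regimen in the meantime. Section 7.1 presents early futility stopping as a protection for subjects. Where the result is already fixed, part of that protection is given up with nothing gained statistically.

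**Working it through.** **Inputs.**
- Stage 1: 15 subjects, futile at 8 or fewer responses (Protocol 7.1, 14.6).
- Null rate 50%: "The null hypothesis that the true response rate is 50% will be tested against the one-sided alternative" (14.6). The alternative is 70%.
- Final rule: "the null hypothesis will be rejected if 27 or more responses (CR + PR) are observed in the first 43 evaluable subjects" (14.6).
- Accrual: 59 subjects (14.6) over 24 months (14.6, PFS power paragraph), so 59/24 = 2.46 per month. Counting only the 54 evaluable subjects gives 54/24 = 2.25.
- Lag: Cycle 6 Day 1 is 5 × 28 = 140 days after Cycle 1 Day 1, about 4.6 months.
- True response rates of 40% and 30% are assumptions. The documents say only that 50% or less is of no interest.
- Each non-response is taken to become final at that subject's own Cycle 6 scan.

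**Step 1: the plan's own figures.** The probability of rejecting at true rate p is the sum over x = 9 to 15 of P(Bin(15, p) = x) × P(Bin(28, p) ≥ 27 − x).
- p = 0.50: 0.0499 (stated 0.05).
- p = 0.70: 0.804 (stated 0.801).

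The design reproduces. P(8 or fewer of 15) is 0.696 at 50% and 0.131 at 70%.

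**Step 2: when the result is fixed.** At most 8 responses means at least 15 − 8 = 7 non-responses. Let T be the position, among the 15, of the seventh non-responder:

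P(T = k) = C(k − 1, 6) × (1 − p)^7 × p^(k − 7), for k = 7 to 15.

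The look is futile exactly when T ≤ 15.

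**Step 3: enrolments while waiting.** With steady accrual and the same lag for everyone, the number enrolled between subject T's Cycle 6 scan and subject 15's averages 15 − T. The accrual rate cancels.

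| True response rate | P(futile) | Mean T, given futile | Mean avoidable enrolments, given futile | Unconditional mean |
|---|---|---|---|---|
| 50% (design null) | 0.696 | 12.0 | 3.0 | 2.1 |
| 40% (assumed) | 0.905 | 11.1 | 3.9 | 3.6 |
| 30% (assumed) | 0.985 | 9.9 | 5.1 | 5.0 |

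At 50%, T = 15 in 13% of futile looks, so nothing is saved in those, and T ≤ 13 in 72%. Simulation with random arrivals at 2.25 and at 2.46 per month gives the same conditional means: 3.0, 3.9 and 5.1.

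**Step 4: share of the whole overrun.** During the lag 2.46 × 4.6 = 11.3 subjects enrol, so 15 + 11.3 = 26.3 are in the study when the fifteenth scan is due. With an early call the figure is 26.3 − 3.0 = 23.3, 26.3 − 3.9 = 22.4 or 26.3 − 5.1 = 21.2. About 6 to 8 subjects beyond 15 would still be enrolled.

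**Step 5: sensitivity.** If some non-responses are already final at Cycle 3, the avoidable number grows. At a 50% rate it is about 4.1 if a quarter of failures are known then, and about 5.5 if half are.

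**Step 6: who counts.** Suppose, as an illustration, that the true rate is 50% among all dosed subjects and that 10% fail before any Cycle 6 scan. Under the Section 14 definition those subjects are outside the set, so the rate among those counted is 0.50/0.90 = 0.556 and P(8 or fewer of 15) is 0.53. If they are counted as non-responders, it is 0.70. The choice of who counts therefore changes the decision rule.

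**The case against.** The strongest reply is that nothing is wrong statistically. The error rates reproduce, a two-stage rule is ordinarily written with the first stage assessed in full, and stopping early on a settled count is an optional refinement. That stands: this is an efficiency and exposure point, not an error.

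Section 7.6 also allows the sponsor to stop at any time, and in an open-label trial the responses are visible as they are entered. That stands in part. The ability to stop exists, but a discretionary power is not a pre-specified trigger.

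Three stronger readings are tempting, and the documents do not support them:
- A reader might blame the timing of the look for all 26 enrolments. Most of the overrun comes from the openly stated choice not to pause accrual during the 140-day lag.
- A reader might treat everyone who progresses or dies without response as a non-responder and assume that nothing else changes. The Section 14 set requires a Cycle 6 assessment, and Step 6 shows that such counting moves the chance of a futile result.
- A reader might see a safety failure. Futility here means a response rate of 50% or less, an efficacy benchmark drawn from single-agent rituximab data. Section 14.7 has separate stopping rules for adverse events, and Section 12.5 provides safety committees.

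Finally, SAP Sections 5.2 and 8 record termination with 5 treated patients and no futility analysis. The point therefore had no effect on this trial as run.

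**Conclusion.** The point holds as a minor weakness of the planned design. Given a futile look, waiting for all 15 Cycle 6 scans enrols on average about 3.0 avoidable subjects at the design's null rate, and 3.9 or 5.1 at assumed rates of 40% or 30%. These are conditional means. In a single trial 15 − T can be anything from 0 to 8.

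The figures rest on steady accrual, a constant 140-day lag, non-response becoming known only at Cycle 6, and every counted subject having a Cycle 6 assessment. Type I error (0.0499) and power (0.804) are unaffected by an early call, provided it is made within the Futility Analysis Set as defined.

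**What to change.** In Protocol Sections 7.1 and 14.1, state that futility is declared and enrolment closed as soon as 7 of the first 15 subjects in the Futility Analysis Set, as defined in Section 14, are established non-responders through their Cycle 6 assessment. Otherwise the decision is made at the fifteenth subject's Cycle 6 assessment. Data on the remaining stage-1 subjects are still collected and reported.

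The cost is one sentence and a running response count. The decision and the error rates stay the same.

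Counting subjects who progress or die before a Cycle 6 scan is a separate change. Section 7.1 speaks of the first 15 subjects, while Section 14 admits only those with a Cycle 6 assessment. The two must be reconciled first, and the error rates restated for whichever definition is kept.

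Because the study has ended, the change matters only if this design is used again.
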